8.7.6 Interim analysis for futility

An interim statistical analysis for futility is planned for Part 2, Arm 1A and Arm 1B based on the Simon's two-stage design (Simon, 1989 [5], see Section 6).

Simon's two-stage design based on the Minimax approach will be used for Arm 1A and Arm 1B separately. The null hypothesis that the true response rate is 5% will be tested against a one-sided alternative.

In the first stage, 20 patients will be enrolled. Enrollment will continue until the SRC decision and 13 additional patients may be accrued for a total of 33.

The interim analysis will be performed based on all available data from a clinical data cut-off that will occur when the required number of patients in the respective arm (Arm 1A and 1B) have performed the first post-baseline tumor assessment based on PCWG3 or discontinued before; tumor assessment scheduled every 8 weeks for the first 24 weeks and every 3 months thereafter.

One interim analysis is planned, where the decision for both treatment Arms 1A and 1B will be made.

If there are 1 or fewer responses in the first 20 patients in Part 2, Arm 1A or Arm 1B, the enrollment for that arm may be stopped. In case there are no responses reported in the first 19 patients in the respective treatment arms, the sponsor will check and decide if enrollment should stop for futility and no 20th patient to be included.

A patient will be considered as a responder if the best objective response per PCWG3 is CR or PR. All other patients or patients without any post-baseline tumor assessments will be considered as non-responders. Interim analysis will be performed on the mITT set.

A predefined set of TFLs to be generated for the interim analysis is defined in Section 11.

After the interim analysis performed in August 2022 (using a data cut-off date = 01 JUN 2022), the sponsor decided to stop enrollment of mCRPC patients in Part 2 Arms 1A and 1B.

8.8 Pharmacodynamic analyses

Blood samples and tumor samples for biomarker analysis are collected from patients with mCRPC (Part 1 and Part 2 Arms 1A and 1B) and LPC (Part 2 Arms 2 and 3) at time points shown in the SoA (see Section 13.6). Biomarker and pharmacodynamics parameters are analyzed by different laboratories (central laboratory and speciality laboratories).

8.8.1 Pharmacodynamic parameters

Clinical and immunological parameters assessed by qualified assays will be measured as part of Pharmacodynamic set and correlated with clinical response and outcome. As part of this SAP, the following listings will be provided for the Pharmacodynamic set:

Blood	Hormones (Testosterone):
	Cytokines: Interferon Alpha, Interleukin 6, Interleukin 10, Interferon Gamma, Interferon Gamma-induced Protein 10, Tumor Necrosis Factor alpha
	Tumor response and extension

Tissue (only available for LPC patients)	Immune cell infiltration in tumor bed
--	---------------------------------------

8.8.2 Exploratory Biomarker Analyses

Cellular immune responses and further immunological parameters will be analyzed as part of exploratory objective to identify potential predictive, pharmacodynamic, anti-tumor and safety biomarkers indicating activity of W_pro1 monotherapy or in combination with cemiplimab. The analyses except those for cytokines are not part of this SAP.

Table 8-1 provides an overview of the biomarker parameters:

Table 8-1: Biomarker Assessment - Overview

Rationale	Test
Safety	Cytokines: Interferon Alpha, Interleukin 6, Interleukin 10, Interferon Gamma, Interferon Gamma-induced Protein 10, Tumor Necrosis Factor alpha
MoA/PD	Cellular immune response (Immunogenicity by Post IVS ELISpot)
MoA/PD	HLA typing: HLA DP Beta1 Antigen, HLA DQ Beta1 Antigen, HLA DR Beta1 Antigen, HLA Class IA Antigen, HLA Class IB Antigen, HLA Class IC Antigen. Tumor associated antigen profile (PSA, ACPP, HOXB13, KLK2, NKX3-1)
MoA/PD	T cell profiling, TCR discovery & profiling, Reverse Immune Monitoring,
MoA/PD	Tumor composition, mutation burden & transcriptome (RNA)

HLA = human leukocyte antigen; ICS = intracellular cytokine staining; MoA/PD = mechanism (mode) of action/pharmacodynamics; TCR = T cell receptor.

The following exploratory endpoints based on biomarkers and pharmacodynamics parameters will be analyzed:

- Status of tumor mutational burden and immune-related gene expression (at the RNA level) in tumor tissue prior to treatment.
- Change in protein expression pattern/levels of tumor microenvironment markers (e.g., CD3, CD8, MHC-I, PD-L1, etc.) and prostate tumor markers (e.g., PSA, PSAP, NKX3-1, etc.) in tumor tissue post-treatment compared to baseline.
- Baseline status or change in RNA target expression of W_pro1–encoded antigens in the post-treatment tissue compared to baseline.
- Change in T cell clonality/diversity post-treatment compared to baseline.
- Changes in blood biomarkers prior to and during trial treatment.

These exploratory biomarker and pharmacodynamics analyses are not part of this SAP.

The respective analysis will be specified and performed in the context of the exploratory BioNTech biomarker report.

8.9 Safety analyses

Safety data that will be summarized include extent of exposure, AEs, occurrence of DLTs during Part 1, clinical laboratory assessments, vital signs and body weight, ECGs, physical examination and ECOG performance status (ECOG PS). All safety analyses will be based on the safety set and will be summarized by treatment groups, and for several combined treatment groups as defined in Section 13.4, unless otherwise stated.

Patients will be assigned to the treatment groups according to the actual treatment they have received (“as treated”).

All safety data will be listed for the safety set.

8.9.1 Primary safety endpoints dose-limiting toxicities and treatment-emergent adverse events

The primary endpoint is the occurrence of DLTs and TEAEs reported by relationship, grade, and seriousness according to NCI CTCAE v5.0. The number and percentage of patients with any DLT only for Part 1, and/or TEAEs in Part 1 and Part 2 will be presented.

Moreover, a patient listing will be provided with all relevant dose exposure data of all patients enrolled into Part 1 and Part 2, and a listing of all recorded DLTs and/or AEs will be presented including the reported term and SOC and PT terms coded using MedDRA®, its time of onset, relationship, NCI CTCAE grade, and seriousness including dose exposure data (e.g., W_pro1 DL).

The respective analyses are specified in Section 8.9.3.

8.9.2 Extent of exposure

The following dose-exposure variables will be derived and analyzed for each IMP compound (W_pro1 and cemiplimab). The respective analyses for ADT are depending on the different kinds of ADT administered during the trial and will be defined at a later stage:

- Number of cycles (Total)
- Number of cycles with W_pro1, Number of cycles with cemiplimab, Number of ADT administrations
- Number of patients who stopped Part 2 mCRPC W_pro1 and switch to cemiplimab monotherapy
- Actual Treatment duration (weeks) for each compound defined as follows:
(Date of last administration - date of first administration +1 + planned duration)/7, whereas the planned duration (days) is defined as the planned time between two consecutive administrations.
Planned duration for cemiplimab is 21 days (to be used for the calculation of actual treatment duration).
Planned duration for W_pro1 in the first 2 cycles is 7 days because there are 3 treatment administration planned (one every 7 days). Starting from Cycle 3 onwards,

the planned duration of W_pro1 is 21 days (only one treatment administration per cycle). To be used for the for the calculation of actual treatment duration.

ADT: Treatment duration (weeks): (Date of last administration - date of first administration + 1) / 7.

- Actual Cumulative Dose (μg) is defined as sum of all administered doses separate for W_pro1 (μg), cemiplimab (mg) and ADT (mg).

Dose Intensity (DI), Relative Dose Intensity (RDI), planned cumulative dose and planned treatment duration for W_pro1 and cemiplimab are defined as follows:

- DI is defined as Cumulative Dose (μg)/Treatment Duration (weeks)
- RDI is defined as follows:

$$\text{RDI (\%)} = \frac{\text{Actual Dose Intensity } \left(\frac{\mu\text{g}}{\text{week}} \right)}{\text{Planned Dose Intensity } \left(\frac{\mu\text{g}}{\text{week}} \right)} \times 100 = \text{DI} \times \text{TI} \times 100,$$

whereas

$$\text{(Actual) Dose Intensity } \left(\frac{\mu\text{g}}{\text{week}} \right) = \frac{\text{(Actual) Cumulative Dose } (\mu\text{g})}{\text{(Actual) Treatment Duration (weeks)}}$$

$$\text{Planned Dose Intensity } \left(\frac{\mu\text{g}}{\text{week}} \right) = \frac{\text{Planned Cumulative Dose } (\mu\text{g})}{\text{Planned Treatment Duration (weeks)}}$$

$$\text{Dose Index (DI)} = \frac{\text{Total Administered Dose } (\mu\text{g})}{\text{Total Planned Dose } (\mu\text{g})}$$

$$\text{Time Index (TI)} = \frac{\text{Planned Treatment Duration (weeks)}}{\text{Actual Treatment Duration (weeks)}}$$

Planned cumulative dose for W_pro1 and cemiplimab compounds is defined as follows:

- The planned dose of W_pro1 is $\text{CCI} \mu\text{g}$ ($\text{CCI} \mu\text{g} + \text{CCI} \mu\text{g} + \text{CCI} \mu\text{g}$) for Cycle 1, $\text{CCI} \mu\text{g}$ $\text{CCI} \mu\text{g} + \text{CCI} \mu\text{g} + \text{CCI} \mu\text{g}$) for Cycle 2, and $\text{CCI} \mu\text{g}$ for all following cycles. In the case a patient has attended 5 cycles, the planned cumulative dose for W_pro1 is $\text{CCI} \mu\text{g}$, irrespectively if the patient has been treated at each cycle or not.
- The planned dose of cemiplimab is CCI mg per cycle. In the case a patient has attended 5 cycles, the planned cumulative dose of cemiplimab is CCI mg, irrespectively if the patient has been treated at each cycle or not.

Planned treatment duration (weeks) for W_pro1 and cemiplimab is defined as follows:

- W_pro1 and cemiplimab:
Planned duration per cycle is 21 days.
Planned treatment duration (weeks) = (number of cycles * 21)/7, irrespectively if the patient has been treated at each cycle or not.

For patients who did not receive any amount of a compound, the dose exposure parameters for that treatment (number of cycles, duration of treatment, cumulative dose, dose intensity, and relative dose intensity) will be set to 0.

Additionally, the relative dose intensity will be presented categorically (i.e., number and percentage of patients with relative dose intensity of < 60%, 60 - < 80%, 80 - < 90%, 90 - < 110%, ≥ 110%). Moreover, the number and percentage of patients with any dose delay, with any dose modification, and any dose interruption by compound will be presented.

All data will be listed.

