#### **Treatment Exposure**

The following dose exposure variables will be derived and analyzed for each compound:

- Number of cycles
- Treatment duration (weeks) defined as follows:
  - (Date of last administration date of first administration + planned duration)/7, whereas the Planned Duration (days) is defined as the planned time between two consecutive administrations.
- Cumulative Dose (μg [BNT112] / mg [cemiplimab]) defined as sum of all administered doses
- Dose Intensity (DI) defined as Cumulative Dose/Treatment Duration
- Relative Dose Intensity (RDI) defined as follows:

RDI (%) = 
$$\frac{\text{Actual Dose Intensity}}{\text{Planned Dose Intensity}} \times 100 = \text{DI x TI x 100},$$

whereas

(Actual) Dose Intensity = 
$$\frac{\text{(Actual) Cumulative Dose}}{\text{(Actual) Treatment Duration}}$$

CONFIDENTIAL Page 86 of 122

 $Planned\ Dose\ Intensity = \frac{Planned\ Cumulative\ Dose}{Planned\ Treatment\ Duration}$ 

 $Dose\ Index = \frac{Total\ Administered\ Dose}{Total\ Planned\ Dose}$ 

 $Time\ Index = \frac{Planned\ Treatment\ Duration}{Actual\ Treatment\ Duration}$ 

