Dosage regimen:	
One cycle (C) is defined as 21 days.
 
The patients will receive the following treatments in the following dose and schedule:
 
Part 1 and Part 2 Arms 1A and 1B (mCRPC)
 
 IV administration of W_pro1 on Day (D)1/8/15 of C1 (intra-patient dose titration) and C2, thereafter starting with D1 of C3 every 3 weeks (Q3W) until end of treatment criterion is met. Part 1/Dose Titration

	
 - Three doses of W_pro1 will be used for an intra-patient dose titration during C1: CCI µg, CCI µg, and CCI µg of total RNA, comprising CCI µg, CCI µg, and CCI µg of RNA of each of the 5 antigens encoded by the W_pro1, respectively. • Part 2/Expansion 
 - REDR was selected after the review of individual and cumulative safety data, and preliminary pharmacodynamic data of Part 1 by the Safety Review Committee (SRC). The selected dose range consists of a starting first dose of W_pro1 of CCI µg, with an intra-patient dose titration to CCI µg in the second dose, and CCI µg of total RNA in the next doses. Total RNA of CCI µg, CCI µg and CCI µg comprise CCI µg, CCI µg, and CCI µg of RNA of each of the 5 antigens encoded by the W_pro1, respectively. - Part 2 Arm 1A: Cemiplimab CCI mg IV Q3W. - Part 2 Arm 1B: Following progression after W_pro1 monotherapy, patients have the option to be treated with cemiplimab CCI mg IV Q3W monotherapy. 
Part 2 Arms 2 and 3 (LPC) – Part 2/Expansion ONLY
 
 • IV administration of W_pro1 on D1/8/15 of C1 (intra-patient dose titration) and C2, thereafter starting with D1 of C3 in a Q3W schedule until C8 followed by radical prostatectomy. • Part 2 Arm 2: Cemiplimab CCI mg IV Q3W.

Duration of treatment:
	
 • Part 1 and Part 2 Arms 1A and 1B (mCRPC): The treatment with W_pro1 will last until unacceptable toxicity or disease progression. • Part 2 Arms 2 and 3 (LPC): The treatment with W_pro1, cemiplimab will last until unacceptable toxicity or disease progression, or up to C8. • If either W_pro1 or cemiplimab needs to be discontinued, treatment with either cemiplimab or W_pro1 can continue upon investigator’s and sponsor’s agreement. • If treatment with ADT (e.g., goserelin acetate) needs to be discontinued, cemiplimab and/or W_pro1 also need(s) to be discontinued.

IMP 2:	Cemiplimab (LIBTAYO)

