7 ANALYSIS SETS AND SUBGROUPS

7.1 Analysis sets

The following analysis sets are defined:

Population	Description
Screened	The screened analysis set is defined as all patients who sign the informed consent form (ICF).
Intent-to-Treat (ITT)	Part 1: The ITT set is defined as all patients to whom IMP is assigned. Part 2: The ITT set is defined as all patients who are randomized to the IMP.
Modified Intent-to-Treat (mITT)	Part 1: The mITT set is defined as all patients to whom IMP is assigned and have a baseline and at least one post-baseline (i.e., one on-treatment or post-treatment) tumor assessment (clinical or imaging assessment). Part 2: The mITT set is defined as all patients who are randomized to the IMP and have a baseline and at least one post-baseline (i.e., one on-treatment or post-treatment) tumor assessment (clinical or imaging assessment).
Safety (SAF)	The safety set is defined as all patients who have received IMP (i.e., at least 1 dose of W_pro1 and/or cemiplimab).
DLT Evaluation	Only applicable for Part 1: The DLT evaluation set includes all patients from the safety set who either have completed the DLT evaluation period and meet the minimum exposure criterion or have experienced a DLT during C1. Patients who do not experience any DLTs during C1 are considered to be evaluable if they have been observed for a minimum of 21 days following the first dose and are considered to have sufficient safety data to conclude that a DLT did not occur. A patient is considered to have met the minimum exposure criterion if the relative dose intensity of W_pro1 in C1 is at least 90%.
Per Protocol (PP)	The per protocol (PP) set is defined as all patients who have received IMP and fulfil the following criteria: 
 • The absence of any important protocol deviations that could affect the primary efficacy analysis • The completion of a minimal exposure to the treatment of 1 cycle • Availability of baseline and at least one on-treatment / post-treatment tumor assessment Important deviations will lead to an exclusion of patients from the PP set and will be agreed at the data review meeting (DRM) prior to database snapshot for the final analysis. Protocol deviations that may be considered important will be specified in the SAP (see Section 7.2)

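### The SAP adds a day to actual but not to planned treatment duration, so a fully dosed, on-schedule patient falls short of 100% relative dose intensity (95.5% after one cycle)

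*SAP*

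**What the plan says.** SAP 8.9.2 computes actual treatment duration in weeks, separately for W_pro1 and cemiplimab, as ("Date of last administration - date of first administration +1 + planned duration)/7". The planned duration inside that formula is the interval between consecutive administrations. For W_pro1 the SAP states "Planned duration for W_pro1 in the first 2 cycles is 7 days because there are 3 treatment administration planned (one every 7 days"); it is 21 days from Cycle 3 onwards, and 21 days throughout for cemiplimab.

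The duration it is compared with is defined in the same section: "Planned treatment duration (weeks) = (number of cycles * 21)/7". RDI is the Dose Index (administered over planned dose) times the Time Index (planned over actual duration).

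Protocol 9.4.5, under Treatment Exposure, gives the same actual-duration formula without the extra day; it ends "date of first administration + planned duration)/7".

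RDI is used in two ways. It is an exploratory endpoint (Table 3-1 in both documents), summarised overall and in bands with cuts at 60, 80, 90 and 110%. It also gates the DLT evaluation set in SAP 7.1, where a patient without a DLT has met the "minimum exposure criterion if the relative dose intensity of W_pro1 in C1 is at least 90" per cent. Protocol 9.3 sets the same cut-off. SAP Appendix 1 (13.1), which records changes to the protocol-planned analyses, does not mention the duration formula.

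**The concern.** There are two usual ways to count treatment duration. One counts calendar days inclusively from first to last dose, which needs one added day. The other takes the difference in dates and adds the interval that the last dose is meant to cover. The SAP formula does both, so the day of the last dose is counted twice. Because the planned duration is a plain multiple of 21 days, the two sides of the Time Index are on different bases and the ratio is below 1 for a patient who did exactly what was planned.

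Two things are at stake. The RDI summaries would understate adherence, most of all in patients with few cycles. And because Cycle 1 RDI has a fixed 90% cut-off, the SAP and the protocol could classify the same Part 1 patient differently, with no recorded reason for the difference.

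**Working it through.** The documents state no RDI value for an adherent patient, so there is no plan figure to reproduce. The check applies the definitions directly.

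**Inputs**
- Cycle 1 dosing days: "IV administration of W_pro1 on Day (D)1/8/15 of C1 (intra-patient dose titration) and C2" (SAP 3.2), so last minus first dose is 14 days on schedule.
- Trailing interval for W_pro1: 7 days in Cycles 1 and 2, 21 days afterwards; for cemiplimab 21 days (SAP 8.9.2).
- Planned duration: 21 days per cycle (SAP 8.9.2).
- Dose Index: taken as 1 (full dose). The dose amounts are redacted, but they cancel.
- The SAP gives no separate Cycle 1 formula, so the general one is applied to Cycle 1 alone.

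**Cycle 1, full dose.** RDI = 21 / actual days × 100. Actual days on schedule are 14 + 1 + 7 = 22 under the SAP and 14 + 7 = 21 under the protocol. Only the gap between first and last dose counts; a late Day 8 dose with Day 15 on time changes nothing.

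| Last C1 dose late by | SAP | Protocol |
|---|---|---|
| 0 days | 21/22 = 95.5% | 21/21 = 100.0% |
| 1 day | 21/23 = 91.3% | 21/22 = 95.5% |
| 2 days | 21/24 = 87.5% | 21/23 = 91.3% |
| 3 days | 21/25 = 84.0% | 21/24 = 87.5% |

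At full dose the two formulas fall on opposite sides of 90% only in the 2-day row. Day 15 has a window of ±1 day (Protocol 1.3), so that row is out of window.

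**More cycles, full dose and on schedule.** Under the protocol formula, actual days after n cycles equal 21n (for example, 35 + 7 = 42 at n = 2 and 42 + 21 = 63 at n = 3). The SAP adds one day, so RDI = 21n/(21n + 1):
- n = 2: 42/43 = 97.7%
- n = 3: 63/64 = 98.4%
- n = 5: 105/106 = 99.1%
- n = 8: 168/169 = 99.4%

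Cemiplimab gives the same values: 21(n − 1) + 1 + 21 = 21n + 1 days.

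**Dose Index needed to reach 90% in Cycle 1**
- On schedule: SAP 0.9 × 22/21 = 94.3%; protocol 0.9 × 21/21 = 90%.
- Last dose 1 day late (in window): SAP 0.9 × 23/21 = 98.6%; protocol 0.9 × 22/21 = 94.3%.

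**Band changes.** SAP RDI equals protocol RDI × D/(D + 1), where D is the actual number of days under the protocol formula. A patient moves from the 90 to <110% band to the band below if the protocol RDI is at least 90% but under 90% × (D + 1)/D. That upper limit is 90 × 22/21 = 94.3% at D = 21 and 90 × 169/168 = 90.5% at D = 168.

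**The case against.** The best defence of the formula is that SAP 8.2 defines durations generally as last minus first date plus one, and that the protocol leaves technical detail to the SAP. This does not rescue it. The general rule adds no trailing interval, and neither does the SAP's own ADT formula, which uses the extra day alone. The planned duration was not put on a matching basis either.

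The objections to the size of the consequence are stronger, and they stand:
- RDI is exploratory and descriptive. No hypothesis test uses it, and the on-schedule values (95.5% to 99.4%) share a band with 100%.
- No fully dosed patient treated within the visit window fails the 90% gate: the worst case is 91.3%. Longer delays are allowed for managing adverse events (Protocol 6.6.1.2), so a 2-day delay is possible, but nothing in the documents shows that one occurred.
- The gate covers only Part 1 (9 patients dosed), only those without a DLT, and only W_pro1. The cemiplimab error has no gate consequence.
- The planned DLT outputs, Table 14.3.1.29 and Listing 14.3.2.4, are assigned to the Safety set, although SAP 7.1 assigns DLT evaluation to the DLT set. On the listed outputs the effect would appear mainly in the analysis-set counts and exclusions (SAP 8.5), not in DLT counts.

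A reader might infer that the extra day bears on the dose range taken into Part 2. The documents do not support that. The Safety Review Committee reviewed Part 1 on 17 May 2021 (Protocol 2.3 and 4.4), SAP version 1.0 was approved on 18 October 2021, and SAP Section 5 places the committee's review material outside the SAP.

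**Conclusion.** The formula is wrong as written and conflicts with the protocol without a record of the change. It lowers every non-zero RDI for W_pro1 and cemiplimab. At full dose and on schedule the shortfall is 4.5 percentage points after one cycle and 0.6 after eight, so it is largest in patients who stop early. Patients with a true RDI just above 90% can move down a band.

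It could change who belongs to the Part 1 DLT evaluation set, through a last Cycle 1 dose 2 days late at full dose, or through a modest dose shortfall on schedule (Dose Index from 90% to just under 94.3%). Whether any of the nine patients is in either position cannot be told from the documents, so a reader should not conclude that the set has in fact changed. The dose-range decision is untouched.

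This rests on applying the general formula to Cycle 1 alone and on a Dose Index of 1 where stated. Severity is minor.

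**What to change.** Delete the added day from the actual-duration formula for W_pro1 and cemiplimab in SAP 8.9.2, so that it matches Protocol 9.4.5. Leave the ADT formula as it is, since it has no trailing interval. Then recompute the RDI tables and listings and re-derive membership of the Part 1 DLT evaluation set, noting any patient whose status changes.

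If the sponsor does intend the added day, planned duration must be put on the same basis and the change listed in SAP Appendix 1.

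The cost is one SAP edit, a change to the derivation program and a rerun of the exposure and analysis-set outputs. No new data are needed.

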#### Specific inclusion criteria for newly diagnosed LPC patients (Part 2 Arms 2 and 3)

- 14. Treatment-naïve patients with LPC (i.e., N0, M0). According to risk levels of the European Association of Urology Guidelines on Prostate Cancer (2018) and in line with the US National Comprehensive Cancer Network (NCCN 2020) patients must have at least one of the following:
  - a. PSA > 20 ng/mL or
  - b. Gleason Score >7 or
  - c. Localized stage ≥cT2c, N0, M0 according to tumor, node, metastasis (TNM) classification
- 15. Patients who intend to have and are suitable for a radical prostatectomy.
- 16. Patients must have adequate liver function defined as:
  - a. Total bilirubin  $\leq 1.5 \times \text{ULN}$  ( $\leq 3 \times \text{ULN}$  is acceptable for patients with known Gilbert disease)

CONFIDENTIAL Page 54 of 122

- b. AST and ALT  $\leq 2.5 \times ULN$
- 17. Patients must agree to provide tumor sample(s) from pre-treatment diagnostic biopsy and planned post-treatment surgery.
- 18. Patient must be eligible for up to 6 months of ADT treatment before prostatectomy.

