Composition:	Programmed death receptor-1 (PD-1) blocking antibody
Dosage regimen and duration of treatment:	Refer to above description of IMP1 for dosage regimen and duration of treatment
Non-investigational medicinal product (NIMP):	
Part 2 Arms 2 and 3 (LPC) ADT, e.g., Goserelin acetate subcutaneous (SC) injection at a dose of 10.8 mg every 12 weeks (Q12W) or other ADT according the current prescribing information valid in a given country.	
Product:	Goserelin acetate (Zoladex [®] LA 10.8 mg implant)
Composition:	Goserelin acetate (equivalent to 10.8 mg goserelin)
Administration:	SC
Dosage regimen:	One 10.8 mg depot injection given into the anterior abdominal wall Q12W
Duration of treatment:	Two injections (≤ 7 days C1D1 and 12 weeks after the first injection); treatment will last until unacceptable toxicity or disease progression, or up to C8
Treatment and trial duration	
Treatment and follow-up duration:
 
Part 1 and Part 2 Arms 1A and 1B (mCRPC): mCRPC patients will be treated until a discontinuation-of-treatment criterion is met. One cycle is defined as 21 days. End of treatment (EoT) assessment will be performed up to 21 days after administration of last dose of IMP for patients who discontinued trial treatment, except if patient was lost to follow-up or died.
 
All patients (Part 1 and Part 2 Arms 1A and 1B) will be actively followed up 30 days for safety (D30 Safety FU) after last intake of W_pro1. Patients in Part 2 Arm 1A will be followed up 90 days for safety (D90 Safety FU) after last intake of cemiplimab, or 30 days for safety (D30 Safety FU) after last intake of W_pro1, whichever is later. All patients will be followed up 6 and 12 months after last IMP administration for efficacy.
 
Within 28 days after confirmation of disease progression, patients of Arm 1B can optionally start cemiplimab monotherapy and will follow the Schedule of Activities (SoA) shown in Section 13.6 after performing the EoT for W_pro1 treatment.
 
Part 2 Arm 2 and Arm 3 (LPC):

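### SAP 8.9.2 defines ADT duration without the dosing interval it adds for the IMPs, so the planned two-depot course is reported as 12.1 weeks instead of about 24

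*SAP*

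**What the plan says.** SAP Section 8.9.2 defines actual treatment duration in weeks. For the IMPs the rule is "Date of last administration - date of first administration +1 + planned duration)/7", where the added term is the scheduled gap from one dose to the next. The interval is then fixed for each product. For cemiplimab, "Planned duration for cemiplimab is 21 days (to be used for the calculation of actual treatment duration"). For W_pro1 it is 7 days in Cycles 1 and 2 and 21 days from Cycle 3 onwards.

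Under the same bullet ADT has its own line, without an interval: "ADT: Treatment duration (weeks): (Date of last administration - date of first administration + 1) / 7".

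The opening of the section names W_pro1 and cemiplimab as the compounds covered and adds: "The respective analyses for ADT are depending on the different kinds of ADT administered during the trial and will be defined at a later stage". So the section both postpones the ADT analyses and prints an ADT rule. It is the only duration rule specific to ADT in either document.

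The reference ADT is described in SAP Section 3.2: "One 10.8 mg depot injection given into the anterior abdominal wall Q12W". Two injections are planned, the second "12 weeks after the first injection); treatment will last until unacceptable toxicity or disease progression, or up to C8". Other ADT products are allowed under local prescribing information. For the LPC arms the protocol's inclusion criteria state: "Patient must be eligible for up to 6 months of ADT treatment before prostatectomy".

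The corresponding formula in Protocol Section 9.4.5 also adds the planned interval, without the extra day. It is introduced as applying to each compound but gives dose units only for BNT112 and cemiplimab, so whether it was meant to cover ADT is unclear.

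**The concern.** The SAP's convention for the IMPs is that a dose counts until the next one is due. The ADT line drops that convention for the product with the longest interval in the trial, and gives no reason. A depot intended to act for 12 weeks then counts for a single day if it is the last, or only, injection.

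The figure is likely to be reported. Tables 14.1.6.1 to 14.1.6.3 in SAP Section 11 are titled as exposure to IMP and NIMP, and ADT is the NIMP. The table shells are in a separate document, so which table carries ADT duration cannot be confirmed here.

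What is at stake is a readable account of ADT exposure in Arms 2 and 3. Protocol Section 7.1 calls ADT the backbone treatment for these patients, and it can be expected to contribute to the PSA and tumor responses summarized there. A duration of about half the planned course, printed next to IMP durations built on a different convention, is easy to misread.

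**Working it through.** The documents state no numeric ADT duration, so there is no figure to reproduce. The check is date arithmetic.

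**Inputs**
- ADT interval: 12 weeks = 84 days (SAP 3.2, Dosage regimen).
- Planned course: two injections 84 days apart (SAP 3.2, Duration of treatment).
- Treatment period in the LPC arms: 8 cycles × 21 days = 168 days = 24 weeks.
- Days per month: 30.4375 (SAP 8.2).

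**Rules compared**
- A, SAP ADT line: (last − first + 1)/7.
- B, SAP IMP form applied to ADT: (last − first + 1 + 84)/7.
- C, protocol form applied to ADT: (last − first + 84)/7.

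**Two injections, 84 days apart**
- A: (84 + 1)/7 = 85/7 = 12.14 weeks.
- B: (84 + 1 + 84)/7 = 169/7 = 24.14 weeks.
- C: (84 + 84)/7 = 168/7 = 24.0 weeks.
- Shortfall: 12.00/24.14 = 49.7% against B; 11.86/24.0 = 49.4% against C.

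**One injection**
- A: 1/7 = 0.14 weeks, that is, one day.
- B: 85/7 = 12.14 weeks. C: 84/7 = 12.0 weeks.

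**Timing as in Protocol Section 6.** The synopsis and SAP 3.2 place the first injection within 7 days of C1D1 and the second 12 weeks after the first. Protocol Section 6 gives C1D1 and C5D1. If the first is given 7 days before C1D1 and the second on C5D1, the gap is 91 days:
- A: 92/7 = 13.14 weeks.
- B: 176/7 = 25.14 weeks. C: 175/7 = 25.0 weeks.

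The printed rule therefore gives 12.1 to 13.1 weeks for a complete course, depending on which description is followed. The two descriptions must be reconciled.

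**Size in general.** B minus A is always exactly one dosing interval, however many injections are given. For the 12-week depot that is 12 weeks, before any cap at surgery or data cut-off.

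**Consistency with the rest of the plan**
- 168 days/30.4375 = 5.5 months, in line with the eligibility wording on ADT before prostatectomy. 85 days/30.4375 = 2.8 months is not.
- In Arm 2, eight three-weekly cemiplimab doses give (147 + 1 + 21)/7 = 24.14 weeks under the IMP rule. They would sit beside 12.14 weeks for ADT given over the same period.
- Cumulative ADT dose is also reported: 2 × 10.8 = 21.6 mg. Over 12.14 weeks this implies 1.78 mg/week, against a planned 10.8/12 = 0.9 mg/week.

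**The case against.** The best defense is that the SAP marks ADT exposure as unfinished. Several ADT products are allowed, no single interval fits all of them, and the section says the ADT analyses will follow. First-to-last dosing is a product-neutral placeholder, correctly computed for what it measures and right as it stands for a daily oral product. This stands in part: the issue is one of definition and internal consistency, and the line may be provisional. But the deferral sentence does not withdraw the printed formula, which a programmer would implement, and the reason given for deferring, the variety of products, is exactly what the formula ignores.

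The second objection is that little depends on the figure, and this stands in full. Dose intensity, relative dose intensity, planned dose and planned duration are defined only for W_pro1 and cemiplimab. The only hypotheses under test concern ORR in Arms 1A and 1B. No planned analysis adjusts for or stratifies by ADT duration.

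A reader might infer more: that the table would show LPC patients as not having received their planned ADT, that ADT products would be ranked wrongly, or that the LPC efficacy results would be distorted. The documents do not support these readings. Section 8.9.2 also reports the number of ADT administrations and the cumulative dose, and Listing 16.2.5.3 shows ADT treatment by patient, so a full course is visible as two administrations. No comparison of ADT products is planned. No efficacy result uses the duration.

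Finally, 24 and 12 weeks are upper figures. Protocol Section 7.1 allows surgery at any time during the 6 months, and Section 2.1.3.1 allows ADT to be interrupted before prostatectomy. With a cap at surgery or data cut-off, the proper value for a patient with two injections 84 days apart lies between 12.14 and 24.14 weeks, and for one injection between 0.14 and 12.14.

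**Conclusion.** The point holds as a limited inconsistency in a descriptive variable. Followed as printed, the SAP reports 12.1 weeks of ADT for the planned two-depot course against about 24, and one day for a single depot against about 12 weeks. It is worth correcting because the printed rule gives a misleading figure and the correction is cheap. It does not threaten any conclusion of the trial.

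This rests on three assumptions: the product is the 10.8 mg 12-weekly depot, the interval after the last injection is not cut short by surgery or data cut-off, and the printed line is not replaced when the deferred ADT definitions are written. For other products the understatement equals that product's interval, and the documents do not give those intervals.

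**What to change.** Before the LPC final analysis described in SAP Section 5, make one of two changes in Section 8.9.2:

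- **Preferred.** For depot ADT use the SAP's own IMP form, (last − first + 1 + planned interval of the ADT product given)/7, with 84 days for the 10.8 mg depot. For daily oral ADT use (stop − start + 1)/7. Cap both at the date of surgery or data cut-off. Keeping the extra day aligns ADT with the SAP's IMP rule.
- **Alternative.** Keep the formula and relabel the variable as time from first to last ADT administration, so that it is not read as duration of treatment.

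In either case, reconcile the line with the deferral sentence by stating that it is the final definition or removing it until one is written. Also reconcile the two descriptions of injection timing, which move the result by up to a week.

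The cost is one line of the SAP and its program, with no new assessments. The small downside of the preferred option is an interval lookup from prescribing information for products other than goserelin 10.8 mg.
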